1. PURPOSE AND BACKGROUND

1.1. Purpose

Primary Objective:

To test whether fluoxetine, a selective serotonin reuptake inhibitor (SSRI) previously demonstrated to enhance post-stroke motor recovery, also enhances post-stroke visual recovery in ischemic stroke survivors.

Secondary Objectives:

- (1) To understand whether a putative fluoxetine effect is mediated through a drug-specific mechanism (*e.g.* a fluoxetine-dependent increase in neural plasticity), or rather through indirect mechanisms, such as general improvements in mood and motivation to participate in rehabilitation, resulting from the antidepressant actions of the drug.
- (2) To track the natural history of post-stroke visual recovery using a combination of clinical and radiographic approaches, including standard neuro-ophthalmologic evaluations, measures of retinal nerve fiber layer (RNFL) thickness, visual and general disability measures, neuropsychological testing, and functional magnetic resonance imaging (fMRI).
- (3) To estimate the feasibility of larger future clinical trials studying the effects of various pharmacological or behavioral interventions on the rate and degree of post-stroke visual recovery.
- (4) To use the information gathered from the above objectives to study the physiologic mechanisms of spontaneous post-stroke visual recovery, with the goal of identifying better targets for therapeutic interventions.

1.2. Background

Current strategies in the treatment of ischemic stroke

Despite major advances in acute stroke care over the last two decades, ischemic stroke remains a leading cause of serious long-term disability (1), with 800,000 strokes expected in the United States this year alone. Some form of visual impairment, such as homonymous hemianopia, is present in one to two thirds of all stroke patients (2). Visual impairment, and in particular homonymous hemianopia, is associated with poor prognosis after stroke (3). Complete spontaneous recovery is uncommon (4) although there is some gradual return of visual function due to endogenous repair mechanisms in the first few months (5). At present, there are no proven treatments beyond the first several hours after a stroke that substantially improve functional outcomes. Two decades on, thrombolysis with intravenous (IV) recombinant tissue plasminogen activator (rt-PA) remains the gold standard of acute stroke care in the United States and elsewhere (6). Unfortunately, only 10% of ischemic stroke patients are eligible for this therapy, as the overwhelming majority

of stroke survivors do not present to a hospital within 3 to 4.5 hours of symptom onset. Furthermore, given that not all eligible patients are treated with IV rt-PA (e.g. 77% in 2011) (7), and only 12% of treated patients benefit (6), less than 1% of all ischemic stroke patients may ultimately owe their functional recovery to this time-sensitive treatment. Therapies that enhance recovery beyond the hyperacute stage of the injury have the potential to help a much larger proportion of stroke patients. However, no subacute therapy capable of enhancing post-stroke recovery across the spectrum of stroke etiology, severity, and symptomatology is currently available.

A possible role for SSRIs in improving functional outcomes in stroke survivors

Several lines of evidence suggest that SSRIs, and in particular fluoxetine, may improve functional outcomes in stroke survivors with moderate to severe motor deficits (8). We hypothesize that SSRIs mediate these effects by modulating neural plasticity and promoting cortical reorganization. One of the major shortcomings of previous studies investigating a role for SSRIs in post-stroke functional recovery has been their focus on clinical outcomes at the expense of physiologic outcomes. As a result, it has been difficult to attribute clinical benefits to mechanisms independent of the antidepressant and activating effects of these medications. In the Fluoxetine for Motor Recovery after Acute Ischemic Stroke (FLAME) trial (8), arguably one of the most compelling studies in this field of inquiry to date, the authors were careful to exclude patients with a history of depression and those on antidepressants at the time of their strokes. At 90 days, patients in the fluoxetine group had less depression, suggesting that these patients may have been more motivated to recover, but the apparent clinical benefit from fluoxetine in terms of motor recovery was still significant after the authors adjusted their analysis for the onset of depression during the study period. While suggestive of an independent role for fluoxetine in post-stroke recovery, these results do not constitute direct evidence of a separate, intervenable mechanism by which fluoxetine may enhance the recovery process in a manner independent of its antidepressant actions. Similarly another SSRI, escitalopram, has shown promise in improving post-stroke cognitive outcomes, specifically short-term memory, in ischemic stroke survivors (9), but the authors did not elucidate the physiologic mechanism of this apparent clinical benefit. We hope to resolve this issue by conducting a randomized clinical trial in which we will follow clinical and physiologic outcomes longitudinally in acute ischemic stroke patients with isolated visual field deficits treated with fluoxetine vs. placebo.

Using visual recovery to study the mechanisms of post-stroke functional recovery

The visual cortex offers the ideal model system for testing hypotheses about mechanisms of neural plasticity that may be engaged by SSRIs in the post-stroke recovery period. First, in contrast to motor recovery, motivation probably plays a less prominent role in post-stroke visual recovery, as most spontaneous recovery probably occurs early (10) and rehabilitative interventions typically focus on teaching patients compensatory techniques. Second, it is known that fluoxetine can reopen critical periods of neural plasticity in the adult rodent visual system (11). Third, structure-function relationships in the visual system are well understood. The early visual cortex in particular has a highly regular retinotopic organization. Post-stroke changes in this retinotopic map can be characterized and followed by fMRI. Furthermore, cerebral infarction can lead to retinal ganglion cell degeneration through a retrograde trans-neuronal mechanism (12), providing another window through which post-stroke changes in the visual pathway can be monitored and quantified using non-invasive techniques such as optical coherence tomography (OCT). Our research team has demonstrated expertise in characterizing early visual system organization in clinical populations (13). Thus, we are well positioned to assess whether

any observed effects of fluoxetine on post-stroke recovery are due to quantifiable changes in neuronal survival and neural plasticity.

Potential future directions

Fulfillment of this research program has the potential to alter our clinical approach to ischemic strokes affecting the visual system. In addition, answering these questions in the visual system may have more general implications. An understanding of the dynamics and limits of neural plasticity in the post-stroke visual cortex will likely enable us to formulate and test specific hypotheses about how therapeutic interventions like fluoxetine may promote recovery from ischemic strokes affecting other higher-order cognitive functions, including language, praxis, memory, attention, and executive function.

2. STUDY DESIGN

2.1. Overview

This will be a single-center randomized double-blind placebo-controlled clinical trial in which ischemic stroke patients with isolated hemianopia or quadrantanopia will be identified during their acute hospitalization and randomly assigned to a course of fluoxetine *vs.* placebo for 90 days. Baseline visual function will be assessed during the initial hospital admission using a battery of neurologic, ophthalmologic, behavioral, and radiographic measures. As post-stroke recovery tends to plateau by 6 months, patients will be followed for 6 months and evaluated using the same set of measures at 30 days, 90 days, and 6 months post-stroke in order to determine whether fluoxetine improves visual recovery.

2.2. Rationale for Study Design

Given the growing evidence that SSRIs may improve motor recovery in stroke survivors, we hypothesize that fluoxetine will also enhance post-stroke functional recovery in the visual system. We further hypothesize that this effect will be mediated through a mechanism independent of the antidepressant and activating effects of fluoxetine. In order to investigate these hypotheses, we have designed a clinical trial in which acute ischemic stroke patients with visual field deficits will be randomized in a 1:1 ratio to fluoxetine *vs.* placebo. The degree of improvement in visual function will then be directly compared between the treatment group and the control group. Because visual recovery after stroke usually plateaus in the first 6 months, we have chosen to treat study subjects for 90 days with fluoxetine *vs.* placebo to determine if exposure to SSRIs during the peak time of recovery improves the rate or degree of recovery. This is also the duration of treatment that was used in the FLAME trial (8).

2.3. Rationale for Dosage

Study subjects will be randomized to 20 mg of fluoxetine *vs.* placebo by mouth, taken on a daily basis for 90 days, starting within 72 hours of admission to the hospital. This dosage was chosen because it was shown to have an effect on post-stroke motor recovery in the FLAME trial (8). Furthermore, stroke patients tend to be older and therefore more likely to develop side effects at higher doses of the drug.

3. CHARACTERISTICS OF THE RESEARCH POPULATION

3.1. Subject Characteristics

- a) **Number of Subjects:** The planned enrollment is 40 patients over 12 months in order to achieve a final sample size of 30 subjects, assuming a dropout rate of 25% during the course of the study. This projected sample size and time frame represent a conservative estimate based on the 56 acute ischemic stroke patients who were admitted to Strong Memorial Hospital with an isolated visual field deficit between January 1, 2015 and December 31, 2015. This sample size is comparable to equivalent pilot trials evaluating the efficacy of an approved drug for a novel indication. If any subjects withdraw from the study, they will be replaced to meet this enrollment goal.
- b) **Gender and Age of Subjects:** Men and women between 18 and 85 years of age will be enrolled in the study. Patients older than 85 will be excluded because advanced age is associated with increased risk of adverse side effects from SSRIs. Furthermore, the ability to fixate and produce reliable visual field measurements deteriorates with increasing age.
- c) **Racial and Ethnic Origin:** Subjects of all racial and ethnic backgrounds will be enrolled in the study.
- d) **Vulnerable Subjects:** Subjects who are vulnerable to coercion or undue influence will not be enrolled, including children, pregnant women, students, employees, prisoners, and persons with decisional impairments.

3.2. Inclusion and Exclusion Criteria

- a) **Inclusion Criteria:** Patients between 18 and 85 years of age who are admitted to Strong Memorial Hospital with an MRI-confirmed acute ischemic stroke resulting in a clinically verifiable isolated right-sided or left-sided homonymous hemianopia or quadrantanopia will be eligible for inclusion in the study.
- b) **Exclusion Criteria:**
 - Known hypersensitivity reaction to fluoxetine or other SSRIs
 - National Institutes of Health Stroke Scale (NIHSS) score greater than 5
 - Premorbid modified Rankin Scale (mRS) score greater than 2
 - Premorbid monocular or binocular visual field deficits
 - Premorbid retinopathy or optic neuropathy
 - Premorbid depression
 - History of cognitive impairment, dementia, or neurodegenerative disorder
 - History of seizure disorder
 - History of mania or hypomania
 - History of hyponatremia
 - History of angle-closure glaucoma or elevated intraocular pressure
 - Current alcohol abuse or impaired liver function
 - Current use of an antidepressant medication
 - Current use of a medication likely to have an adverse interaction with fluoxetine
 - Current use of a medication likely to impair post-stroke recovery
 - Contraindication to MRI
 - Pregnancy or lactation
 - Hemorrhagic transformation of the index stroke, resulting in mass effect
 - Enrollment in another clinical trial at the time of the index stroke

3.3. Discussion of Subject Population

In order to minimize risks to our study population, potential subjects will be excluded from participation in the study if they have a known contraindication to a component of the study protocol, such as a drug allergy to fluoxetine or other SSRIs, concomitant use of a medication that may interact with SSRIs, or contraindication to MRI. Because of potential risks to the fetus and nursing infants, pregnant and lactating women will also be excluded. Pre-menopausal women will only be included if the initial urine pregnancy test is negative and they commit to using birth control for the duration of the drug administration phase of the study (first 90 days). Patients with impaired liver function or advanced age (greater than 85 years old) will be excluded due to the possibility of impaired fluoxetine metabolism.

Additionally, we will exclude any subject with a condition that may interfere with the interpretation of the study results, such as premorbid depression, previously identified visual field deficit of any cause, concurrent use of medications known to impair post-stroke recovery, high initial NIHSS score, or hemorrhagic transformation of the index stroke resulting in a hematoma large enough to cause mass effect (corresponding to an ECASS score of PH1 or PH2) (14), as these conditions are associated with poor functional outcome.

Finally, because automated Humphrey perimetry requires the subject to be able to follow multi-step commands and maintain visual fixation for 20 minutes, potential subjects with impaired cognition or attention, or premorbid mRS score greater than 2, will be excluded.

4. SUBJECT IDENTIFICATION, RECRUITMENT, AND CONSENT

4.1. Method of Subject Identification and Recruitment

Potential subjects will be identified by Neurology and Ophthalmology residents, fellows, and attending physicians at Strong Memorial Hospital. When a candidate is identified, a member of the medical team will ask the patient if he or she would be interested in being approached by study personnel during the hospital admission in order to find out more about the study. If the patient expresses interest, the study coordinator and one of the investigators will meet with the patient and family to describe the study and obtain consent. In order to minimize undue influence, members of the medical team (*i.e.* the attending physician of record and the on-service stroke fellow) will not be involved in the consent process. Instead, an investigator not directly involved in the patient's care will be responsible for discussing the study with the potential subject and obtaining consent.

4.2. Process of Consent

An investigator will obtain written informed consent from each subject before the performance of any procedure related specifically to the study protocol. The protocol will be reviewed with each candidate, highlighting the differences between study-specific procedures and routine studies performed as part of standard care, so that he or she can make an informed decision about participation in the study. When possible, potential study participants will be approached early during their hospital course to ensure sufficient time to address any questions or concerns. We do not anticipate enrolling any non-English speaking subjects.

Each signed consent form will be kept in the study binder in a locked drawer in the Principal Investigator's office (Room 5.5722A). This is a locked room in an office suite that requires badge access for entry. A separate fMRI consent form will be used for any fMRI studies performed at the Rochester Center for Brain Imaging (RCBI). This consent will be administered by RCBI staff on the day of the procedure and stored securely in accordance with RCBI protocols.

5. METHODS AND STUDY PROCEDURES

Subjects will be evaluated at five time points as indicated in the Table: at baseline (*i.e.* during the acute hospitalization immediately after enrollment in the study) and at 7 days, 30 days, 90 days, and 6 months after randomization. They will be contacted by phone 7 days after the initiation of the study drug to screen for any adverse events using an adverse event questionnaire (Appendix H). This questionnaire will be administered in the hospital if the patient has not been discharged yet, and repeated at the remaining time points.

At baseline, the premorbid mRS, Patient Health Questionnaire-9 (PHQ-9), and Visual Function Questionnaire-25 (VFQ-25) scores will be determined for each subject. As part of standard care, subjects will undergo a formal neuro-ophthalmological examination to confirm and characterize their visual field deficits. This will also help to rule out ocular, motor, or cognitive deficits likely to impair their ability to perform the visual function tests required by the study protocol. In addition, subjects will be evaluated by ocular coherence tomography to determine baseline RNFL thickness, neuropsychological testing to assess their ability to perform certain visual tasks, and fMRI for retinotopic mapping of the early visual cortex. To ensure that potential subjects do not have any hematologic abnormalities (*e.g.* thrombocytopenia) or metabolic derangements (*e.g.* hyponatremia, hepatic insufficiency) that may affect the safety of taking fluoxetine, all candidates will have a complete blood count (CBC) and comprehensive metabolic panel (CMP) drawn at baseline. Women of childbearing age will have a urine pregnancy test to make sure they are not pregnant. Finally, because some SSRIs like citalopram have been associated with QT interval prolongation, each patient's baseline electrocardiogram (ECG) will be assessed for possible arrhythmias prior to randomization.

Subjects will be started on fluoxetine *vs.* placebo within 5 days of the index stroke and no later than 72 hours after their admission to the hospital. Seven days after randomization, they will be called by telephone and assessed for any adverse events using a questionnaire. If the subject has not been discharged from the hospital yet, this assessment will be performed in person in the hospital. Subjects will return for study-specific and routine evaluations at 30 days, 90 days, and 6 months following the initiation of treatment. During these visits, they will undergo assessments that constitute standard care as well as study-specific evaluations and monitoring, as indicated in the Table.

5.1. Treatment Dosage and Administration

Subjects will be randomized in a 1:1 ratio to 20 mg of fluoxetine *vs.* placebo. Fluoxetine is an oral medication and is usually taken in the morning because of its possible stimulant effects. The University of Rochester Medical Center Investigational Drug Service will prepare and provide fluoxetine or placebo to all subjects. They will administer the study drug to each study participant during the hospital admission. At discharge, each study

participant will be given enough study drug to last until the end of the study. The study drug will be discontinued without a taper at the end of 90 days. Drug accountability logs will be updated during routine follow-up visits at 30 and 90 days.

5.2. Efficacy Assessments

To assess the effect of fluoxetine on post-stroke visual recovery, subjects will be evaluated by a formal neuro-ophthalmologic examination, automated Humphrey perimetry, OCT, neuropsychological testing, fMRI, and various clinical scales and questionnaires (mRS, PHQ-9, and VFQ-25) following the schedule outlined in the Table. Functional vision will be assessed by calculating the functional vision score as described in the Guide for the Evaluation of Visual Impairment, prepared on behalf of the International Society for Low Vision Research and Rehabilitation (15).

1. Modified Rankin Scale (mRS): The most commonly used outcome measure in stroke clinical trials, the mRS is a tool designed to quantify disability in stroke patients based on their level of independence in the activities of daily living (Appendix E). It requires 5 minutes to perform and will be administered by certified faculty, fellows, and residents from the Department of Neurology. Scores range from 0 (no symptoms) to 6 (death). Documentation of the mRS score at baseline and outpatient follow-up is part of standard care.
2. Neuro-ophthalmologic examination: This is a standardized clinical evaluation to be performed by study investigator, [name], at the University of Rochester Flaum Eye Institute. It consists of an external eye exam, pupillary exam, dilated fundoscopic exam, standard neurologic exam, and an evaluation of visual acuity, refraction, color vision, sense of brightness, visual field size, and ocular motility. A baseline neuro-ophthalmologic evaluation represents standard care in the assessment of patients with new visual field deficits attributable to an acute ischemic stroke.
3. Automated Humphrey perimetry: Humphrey perimetry is an automated non-invasive clinical test performed in most routine ophthalmologic evaluations to characterize and monitor a patient's peripheral vision, using normative data from healthy age-matched controls as a reference. In this study, we will use Swedish Interactive Threshold Algorithm (SITA) standard 24-2 visual field testing to assess each subject's peripheral vision at the specified time points. This form of automated Humphrey perimetry requires 7 ½ minutes of testing time. Testing will be performed by a qualified ophthalmic technician or physician at the University of Rochester Flaum Eye Institute. During each test, the subject will place his or her chin on a chin rest, fixate on a central point, and respond with a push-button when he or she sees a test spot presented briefly in the peripheral visual field. Baseline, 90-day, and 6-month assessments represent standard care, whereas the 30-day assessment is for research purposes only.
4. Optical coherence tomography (OCT): This is a standardized non-invasive clinical test that uses light waves to measure the thickness of the RNFL in patients with a wide range of visual problems. It requires 30 seconds of testing time. It will be performed by a qualified ophthalmic technician or physician at the University of Rochester Flaum Eye Institute. OCT is not part of standard care for this patient population.
5. Patient Health Questionnaire-9 (PHQ-9): This is a self-report inventory used as a screening and diagnostic tool for depression (Appendix F). The 9 items are based on

the 9 diagnostic criteria for depression included in the Diagnostic and Statistical Manual of Mental Disorders IV. It takes 5-10 minutes to complete. It will be administered at baseline, 30 days, 90 days, and 6 months. The 30- and 90-day assessments will be performed during routine follow-up in the University of Rochester Stroke and Cerebrovascular Disorders Clinic. The 6-month assessment will be performed by phone interview. Screening for depression by PHQ-2, a shorter version of PHQ-9, is part of standard care for this patient population at baseline. However, screening by PHQ-9 is not part of standard care at baseline or at any other study time point.

6. Functional vision assessment: This will be done by calculating the functional vision score for each subject as described in the Guide for the Evaluation of Visual Impairment (15), a clinical and research tool designed to measure functional vision in adults with acquired vision loss. Calculation of a functional vision score using this tool requires visual field and visual acuity assessments, so it will be done at baseline and at 6 months by study investigator, [name], at the University of Rochester Flaum Eye Institute. Ophthalmologic follow-up at these time points is part of standard care.
7. Visual Function Questionnaire-25 (VFQ-25): This is a 25-item survey designed to provide a vision-targeted assessment of health-related quality of life by measuring the influence of visual disability on daily visual functioning, emotional well-being, and social functioning (Appendix G). It takes 10 minutes to complete. It will be administered at baseline and 6 months. The 6-month assessment will be performed by phone interview. Assessing vision-related quality of life by VFQ-25 is not part of standard care for this patient population.
8. Neuropsychological testing: The neuropsychological assessment will consist of picture naming tasks, face memory tasks, and other simple tests of low- and high-level visual processing, such as indicating whether a stimulus is seen on a screen. The participant's eye position will be monitored using special cameras during certain tests. Some tests will require participants to indicate the location of a stimulus on a screen with their fingers. For these tests, finger position during the pointing motion will be tracked using a special camera system. Neuropsychological testing will be performed at baseline, 30 days, 90 days, and 6 months by study investigator, [name], and members of his laboratory. The baseline assessment will be completed before discharge from the hospital and require approximately 45 minutes. Subsequent sessions will occur at the RCBI and will require approximately 90 minutes each. Neuropsychological testing is not part of standard care for this patient population.
9. Functional magnetic resonance imaging (fMRI): Visual processing will be assessed using fMRI. Dependent measures will consist of high-resolution measurements of cortical thickness and representation, functional activity during visual tasks as measured by blood oxygen level-dependent (BOLD) responses, and measurements of the structural integrity of nerve fibers in the brain using diffusion tensor imaging. Subjects will be asked to view and respond to a visual stimulus according to the specific task description. For example, they may be asked to name common objects depicted in a picture, or estimate the number of dots in a display. Typically subjects will be asked to perform a task in the MRI machine for 45 minutes, although sessions may go up to 70 minutes depending on the comfort and compliance of the study participant. Tasks will be broken up into shorter runs of 5 to 10 minutes in order to

allow participants to rest during the testing session. Scanning will occur on MRI machines at Strong Memorial Hospital, the University of Rochester Stroke and Cerebrovascular Disorders Clinic, or the RCBI. Study integrity will not be compromised by scanning a given patient on different scanners at different times. We will compute contrasts only between experimental conditions tested on the same machine during the same scan, so the key effects we measure will be orthogonal to any scanner variation. Finally, fMRI data will be retained in an anonymized form for future use by other researchers as part of this study.

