5.3. Safety Assessments

Subjects will be instructed to exercise caution when drinking alcohol or taking any previously prescribed sedating medications, such as diphenhydramine or cyclobenzaprine, while on the study drug. Additionally, they will be advised to contact their primary care physicians or the study team before starting any new prescription or over-the-counter medications, or any new herbal or nutritional supplements. Primary care physicians will be provided with a list of medications and supplements to avoid while their patients are on the study drug.

Laboratory studies: A CBC and CMP will be repeated 30 days after the initiation of the study drug to monitor for any hematologic or metabolic abnormalities. This will require a total of 9 mL of blood to be collected from each subject.

ECG: An ECG will be obtained at baseline and at 30 days to measure each subject's QT interval and monitor for QTc prolongation or other arrhythmias.

Adverse event survey: A questionnaire to screen for adverse events will be administered by study personnel at 7 days by phone interview (Appendix H). This 7-day evaluation will be done in person if the patient has not been discharged from the hospital yet. The same questionnaire will be administered when the subjects return to the University of Rochester Stroke and Cerebrovascular Disorders Clinic for their follow-up visits at 30 and 90 days. Finally, the same questionnaire will be administered at 6 months by phone interview.

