9.3. Recording Adverse Events

As specified in the Table, study personnel will screen each subject for adverse events at 7 days, 30 days, 90 days, and 6 months by recording all voluntary complaints of the subject, administering the adverse event questionnaire, and evaluating any available objective clinical findings.

All adverse events, whether observed by study personnel, or elicited from or volunteered by the subject, will be documented. Documentation will include a brief description of the experience, the date of onset, the date of resolution, the duration and type of experience, the severity, any relationship to the study drug, any contributing or alleviating factors, and any action taken with respect to the study drug.

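### PHQ-9 and VFQ-25 move to a phone interview at 6 months although subjects attend in person then, so within-subject change to 6 months may include a mode effect

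*Combined protocol and SAP*

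**What the plan says.** All references are to the combined protocol and SAP.

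- **PHQ-9 (Section 5.2, item 5).** It is described as a self-report instrument and given at baseline, 30 days, 90 days and 6 months. For the middle two: "The 30- and 90-day assessments will be performed during routine follow-up in the University of Rochester Stroke and Cerebrovascular Disorders Clinic". For the last: "The 6-month assessment will be performed by phone interview".
- **VFQ-25 (Section 5.2, item 7).** There are two time points only: "It will be administered at baseline and 6 months. The 6-month assessment will be performed by phone interview". Section 5 defines baseline as "during the acute hospitalization immediately after enrollment in the study".
- **Attendance at 6 months (Section 5).** "Subjects will return for study-specific and routine evaluations at 30 days, 90 days, and 6 months following the initiation of treatment". The Table marks perimetry, OCT, the functional vision score, neuropsychological testing and fMRI at that time.
- **Use of the scores.** Section 13.2 lists both scales as secondary outcomes. It names no analysis for them and does not mention mode of administration.
- **Drug stop (Section 5.1).** Study drug ends at 90 days.

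The documents give no reason for the phone mode. Neither item says whether the form is self-completed or read out at the in-person time points.

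**The concern.** A change score is readable as change only if the instrument is given in the same way at both ends. Here the far end is a phone interview and the near end is in hospital or in clinic. Randomisation does not help with this, because the question is about change within subjects.

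For VFQ-25 the stake is secondary objective 2, which tracks the natural history of visual recovery and counts visual disability measures among its tools. VFQ-25 has no other follow-up point to fall back on.

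For PHQ-9 the stake is secondary objective 1, which asks whether any benefit works through mood. The primary endpoint is read at 6 months, and the PHQ-9 taken at that time is the one collected differently. The switch also falls in the interval that begins when study drug ends. A mood shift seen there in the pooled sample could reflect time, the drug stop or the mode.

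The plan guards against this kind of problem elsewhere: Section 5.2, item 9 limits fMRI contrasts to conditions run on one machine in one scan. The questionnaires have no comparable safeguard.

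**Working it through.** The plan states no figure on this point, so there is none to reproduce. The check is a count, a list of the change scores available, and a short piece of algebra.

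**1. The 6-month column of the Table against the text of Sections 5.2 and 5.3**

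| Row marked at 6 months | Where or how |
|---|---|
| Automated perimetry | In person, Flaum Eye Institute |
| OCT | In person, Flaum Eye Institute |
| Functional vision score | In person, Flaum Eye Institute; needs visual field and acuity |
| Neuropsychological testing | In person, RCBI, about 90 minutes |
| fMRI | In person, one of three scanner sites, 45 to 70 minutes |
| PHQ-9 | Phone |
| VFQ-25 | Phone |
| Adverse event questionnaire | Phone |

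Total: 5 in person + 3 by phone = 8 rows. The in-person count is four only if the functional vision score is treated as derived from other tests.

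**2. Which change scores cross the switch**

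- VFQ-25: two time points give one interval (baseline to 6 months), and it crosses.
- PHQ-9: four time points give three successive intervals. Baseline to 30 days runs from hospital to clinic, and 30 to 90 days stays in one clinic. Only 90 days to 6 months goes from in person to phone. Longer PHQ-9 changes that end at 6 months cross it too.

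**3. What the switch does**

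Let b be the average shift in score from phone rather than in-person administration, and Δ the true mean change. F is fluoxetine and P is placebo.

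- Within an arm: observed change = Δ + b.
- Between arms: (Δ_F + b_F) − (Δ_P + b_P) = (Δ_F − Δ_P) + (b_F − b_P). If b_F = b_P, the shift cancels.

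Illustration with assumed values (true change −2 on fluoxetine and −1 on placebo; none of these figures is in the documents):

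| Assumed b | Fluoxetine, −2 + b | Placebo, −1 + b | Difference |
|---|---|---|---|
| 0 | −2.0 | −1.0 | −1.0 |
| 0.5 | −1.5 | −0.5 | −1.0 |
| 1 | −1.0 | 0.0 | −1.0 |
| 2 | 0.0 | +1.0 | −1.0 |

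A simulation with an assumed SD of 5 and 15 subjects per arm gave the same pattern, with a difference of about −1.0 throughout.

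**4. What a phone fallback would do**

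If shares p_F and p_P of the arms were phoned and the rest seen in person, the between-arm contrast would carry b × (p_F − p_P). Under the present plan p_F = p_P = 1, so the term is zero. With the planned 15 completers per arm (Section 13.1), each one-subject imbalance in phone use adds b/15 = 0.067b. At the assumed b = 2 that is 0.13 points.

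**The case against.** The strongest defence is that the plan's uniform phone contact is clean for the randomised comparison, while a visit with phone fallback makes mode depend on attendance after randomisation, which could differ by arm. This stands. Step 4 shows that the term is small unless fallback is common or lopsided, but recording the mode does not remove it. A sensitivity analysis is therefore part of the fix.

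Second, no stroke-clinic visit and no mRS are marked at 6 months, and the tests then are at other sites. The phone may be a practical choice, so the call cannot be called pointless. Nor do the documents show that it adds missing data, since a call could also reach someone who misses a visit. Even so, subjects are already with study personnel at 6 months, and fallback keeps the phone's reach.

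Third, the baseline mode is implied by the hospital setting and not stated. The change of setting is documented; a change from self-completion to interview is not. The effect can only be called possible. Section 5 also leaves open whether the word premorbid applies to the baseline PHQ-9 and VFQ-25 or to the mRS alone. If it covers VFQ-25, its change score would start from pre-stroke function and would not measure recovery at all.

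Fourth, secondary objective 2 names no mood scale, and the two on-drug PHQ-9 follow-ups share one clinic. Both are correct, and they confine the PHQ-9 point to scores ending at 6 months.

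Two stronger readings are tempting and fail. A reader might infer that the 6-month call contradicts Section 9.3, which asks for "evaluating any available objective clinical findings". That wording covers only what is available, and the same sentence applies to the 7-day contact, which is itself by phone unless the subject is still in hospital. A reader might also extend the change-over-time argument to the adverse event form, of which Section 5.3 says: "Finally, the same questionnaire will be administered at 6 months by phone interview". That form is already given by phone at 7 days, is a symptom checklist, and is not an outcome in Section 13.2.

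**Conclusion.** The point holds for two secondary outcomes: the single VFQ-25 change score, and PHQ-9 change from 90 days to 6 months. In every subject who completes both ends, these mix true change with a possible mode effect. Its size cannot be taken from the documents; any figure for it is an assumption, and nothing in them shows that phone and in-person scores differ.

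It would be wrong to infer that the treatment comparison at 6 months is biased. Under the plan everyone is phoned, so the effect cancels if it is equal in both arms, and nothing in the documents suggests otherwise. The primary endpoint and the sample size do not depend on either form. This is a small improvement to the interpretation of within-subject change, worth making because it costs little.

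**What to change.** - In Section 5.2, items 5 and 7, give PHQ-9 and VFQ-25 at one of the in-person visits already planned for 6 months.
- State the mode (self-completed or read out) and keep it the same at baseline and every follow-up. Clarify in Section 5 whether the baseline scores describe the time before or after the stroke.
- Use the phone only for subjects who cannot attend, and record the mode for each score.
- In Section 13.2, add a repeat of the 6-month PHQ-9 and VFQ-25 analysis without phone-collected scores, and report phone use by arm.

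Cost: by the plan's own timings, PHQ-9 takes 5 to 10 minutes and VFQ-25 takes 10, so 15 to 20 minutes are added to an already long visit. Some mixed-mode data will remain from non-attenders, and the repeat analysis drops those subjects, so it supports the main analysis and does not replace it. If the phone is kept for everyone, the alternative is to state why and to limit inference on the 6-month scores to between-arm contrasts.
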